**Data: 10/10/2018**

## **INTRODUCTION**

It is well known that female pelvic floor weakness and/or pelvic floor dysfunction (PFD) can have both structural and functional effects, such as urinary incontinence, bowel incontinence, pelvic organ prolapse, and dyspareunia and/or sexual dysfunction (Bozkurt et al., 2014, Pierce et al., 2015, Hyakutake et al., 2016, Neels et al., 2016). One of the main risk factors associated with pelvic dysfunction is the reproductive process, including pregnancy and birth. During this process both modifiable and non-modifiable risk factors for PFD can be identified. Chief among the former are the pregestational and full-term body mass index (BMI), weight gain, smoking, the type of birth, the use of forceps, the duration of the first and second stages of birth, the practice of episiotomy and the use of epidural anaesthesia. Among the non-modifiable risk factors (also known as risk indicators), are age at maternity, position of the foetus and circumference of the newborn's head, the weight of the newborn, and the presence/existence of perineal injury, chiefly those which can affect the anal sphincter (Bozkurt et al., 2014, Hyakutake et al., 2016).

Of all these factors, vaginal birth is the chief modifiable risk factor for developing pelvic floor dysfunction, as women in this group are 2.8 times more likely to suffer stress urinary incontinence, and 5.5 times more likely to suffer a prolapse of the pelvic organs, in comparison with those who give birth via caesarean section. These risks increase with instrumental delivery, which seems to be related to the fact that the incidence of injury to the anal musculature is higher in this procedure (Howard & Makhlouf, 2016).

Among the non-modifiable obstetric risk factors, chief is perineal trauma, whether spontaneous or induced (second degree tears or obstetric anal sphincter injuries), which represents one of the most frequent complications associated with birth (85% of puerperal women) (León-Larios et al., 2017), and has a clear influence in the subsequent appearance of PFD (Bose et al., 2017, León-Larios et al., 2017).

Although in recent years the practice of routine episiotomies has decreased in Spain, the percentage remains above the recommendations of the WHO (WHO 1999, Escuriet et al., 2015) at around 40.2% (León-Larios et al., 2017). Within this average there is a disparity between the public and private systems, whereby, according to Escuriet et al. (2015), there has been an increase in the number of

episiotomies in private hospitals. In a study carried out in the United Kingdom, Smith et al. (2013) found a difference in the frequency of episiotomies between primiparae and multiparae, and also in the different degrees of perineal tearing, with the most frequent being second degree tears in both uniparity and multiparity contexts (Smith et al., 2013, Zimmo et al., 2017).

In addition, the risk of suffering more serious perineal trauma, specifically fourth degree tears affecting the anal sphincter and recta mucosa is three times greater among primiparae than multiparae (León-Larios et al., 2017, López et al., 2014, OMS 1999).

Perineal wounds suffered during birth significantly increase the risk of PFD, with a consequent impact on the female population of physical and emotional discomfort, depression, social isolation, avoidance of healthy physical activity, and reduction in productivity and quality of life, and a resultant increase in the demands on the health service (Smith et al., 2013, Bozkurt et al., 2014, Pierce et al., 2015, Hyakutake et al., 2016).

Primary prevention of PFD is therefore essential, and the following interventions have been shown to be effective: (i) perineal massage during pregnancy (from week 34) (Oblasser et al., 2016), which has been found to diminish the number of episiotomies in primiparae, shorten the first and second stages of labour, and to reduce postpartum pain in multiparae (León-Larios et al., 2017); (ii) weight management and prevention of constipation through the promotion of a suitable diet and by doing physical exercise adapted to pregnancy (Davidson et al., 2000, Kyvernitakis et al., 2015); and (iii) pelvic floor strengthening exercises, which help to reduce discomfort (mainly among primiparae) and reduce the risk of urinary incontinence in the third trimester of the pregnancy and after childbirth (Hyakutake et al., 2016, León-Larios et al., 2017).

With respect to exercises for strengthening the pelvic floor, the most common are hypopressive abdominal exercises and the Pilates Method (PM), which focus on developing the musculature of the transverse abdominis and pelvis in order to decrease intra-abdominal pressure (Kyvernitakis et al., 2015). The latter method is an exercise programme holistically encompassing body and mind in a combination of eastern and western techniques, and incorporating movements drawn from traditional and Swedish gymnastics, rehabilitation techniques, martial arts, yoga and dance (Llewellyn et al., 2017).

## **Background**

Pilates is based on the six fundamental principles of breath, concentration, flow, precision, centring and control. It aims for an equilibrium in musculature by reinforcing weak muscles and stretching tight ones, with an emphasis on control, strength, and flexibility. It focuses particularly on the core – the abdominal muscles, vertebral column and pelvic floor, and is thus instrumental in improving body alignment and good posture across the range of movements habitually carried out in daily activities (Guzmán et al., 2013, Shaban et al., 2014, Llewellyn et al., 2017, Navarro & Luján, 2017). Advocates also note that practitioners gain a greater self-awareness of their body image, their range of motion and personal health (Almagiá, 2003), among other benefits (Culligan et al., 2010, Cruz-Ferreira et al., 2011, Shaban et al., 2014). For this reason, Pilates is often recommended generally as a treatment for alleviating back pain (Boix-Vilella et al., 2017).

Given the marked increase in practising Pilates during pregnancy (Wells et al., 2012, Shaban et al., 2014, Llewellyn et al., 2017), various studies have been carried out to evaluate its effectiveness. These include the effect of Pilates in antenatal classes for reducing anxiety about giving birth and in terms of its overall perinatal outcome and the benefits of a Pilates-based exercise programme during pregnancy and birth (Sarpkaya et al., 2018). Also notable in this regard are studies demonstrating the role of Pilates in reducing lumbar pain during the third trimester Maczka & Sass, 2017, Rogríguez-Díaz et al., 2017). With regard to the specific relation of Pilates with PFD, Dias et al. (2017) found a positive impact on the pelvic floor musculature during pregnancy (Oktaviani, 2017), while Muniz de Souza et al. (2017) concluded that the method was a valid means of helping to prevent the dysfunction (Dias et al., 2017).

The starting hypothesis of this study is that the incidence of perineal wounds during childbirth to be lower among those participating in a specially designed Pilates program.

## **THE STUDY**

### **Aim**

The aim of this study is to evaluate the influence of Pilates sessions during pregnancy on the incidence and degree of intrapartum perineal injuries.

### **Design**

A multicentre quasi-experimental study, will be carry out between November 2018 and December 2019 in health centres (HCs) pertaining to two distinct health districts

### **Participants**

A convenience sample of pregnant women attending antenatal classes at health centres in two distinct districts, and meeting the following inclusion criteria:

(i) being registered on an antenatal programme (AP); (ii) giving written consent of participation; (iii) the pregnancy being a singleton; (iv) the pregnancy being low risk; (v) there not being any contraindications for physical exercise (vi) being at least 18 years old.

Women who have missed antenatal appointments, had difficulty in speaking or understanding Spanish, had given birth by caesarean section or declined to participate will be excluded from the study.

### **Interventions**

The study will be carry out in two stages: the first involved finding Pilates trainers to deliver the sessions, while the second collated participant data from both the experimental and control groups. The first phase took place in November 2018, with the collaboration of two trainers in Huelva and one in Seville, all with the same training background. The second phase will be carried out between December 2018 and December 2019 in the corresponding health centres in Huelva and Seville.

In order to eliminate potential bias as a result of the antenatal classes being deliver by health professionals of different categories, only those health centres where classes are deliver by a midwife were selected for the study. The women participat in the corresponding antenatal classes at the respective centres were

then will be invited to participate in the study either to the experimental group (AC + PM) or in the control group (AC only).

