#### **Sample size**

A minimum sample size of 36 women will be projected, for a confidence level of 95% and a power of 80%, considering 49% avoiding episiotomy in the control group in comparison with 98% in the experimental group (Rodríguez et al., 2017), and divided according to a ratio of 2 women in the control group for every woman in the experimental group. This number will increase in case any women dropped out, such that the final number of participants will be 72, of which 24 will be from the experimental group and 48 the control.

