#### **Data analysis**

The quantitative variables will be presented with the mean and standard deviation, while the qualitative data will be given in frequencies and percentages.

In order to measure the goodness of fit of the quantitative data to a normal distribution, a Lilliefors corrected Kolmogorov-Smirnov test will be used. Bivariate analysis will be carried out with Student's t-test for the comparison of two means. In the case of the qualitative data, the Chi-square test will be used, except when Fisher's exact test was required. Likewise, for the analysis of three or more means, a repeated measures ANOVA will be used to evaluate the effects of the

treatment in the two groups, at baseline, three and five weeks. Correlation between the quantitative variables will be verified using the Pearson coefficient correlation ( $r$ ). Finally, in order to allow for the possibility that the data did not meet the criterion of normality or homoscedasticity, non-parametric versions of the tests above will be also carry out.

Binary logistic regression models adjusted for various qualitative and quantitative predictive variables will be calculated in order to determine association of the variables with perineal trauma in childbirth.

The Odds Ratios (ORs) will be determined with a confidence interval of 95%. The goodness of fit tests ( $-2 \log$  likelihood, goodness of fit statistic, Cox and Snell  $R^2$ , Nagelkerke  $R^2$  and Hosmer–Lemeshow) will be calculated to evaluate the overall fit of the model.

In all statistical analyses, alpha will be set to below 5% / the significance level was established at 5% ( $p < 0.05$ ) and a confidence interval of 95% will be computed. All statistical calculations will be made using IBM SPSS Statistics version 25.0.

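### District is not named in the analysis of a non-randomised two-district study, so a difference in district mix could be read as a Pilates effect, and possible trainer clustering is not addressed

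*Combined protocol and SAP*

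**What the plan says.** The Design and Participants sections describe a multicentre quasi-experimental study with a convenience sample from health centres in two districts. Under Interventions, Pilates is delivered by "two trainers in Huelva and one in Seville", and women attending antenatal classes at the centres are invited into one group or the other. No randomisation is described, and no rule fixes the ratio of the groups within a district or centre.

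Sample size sets a "ratio of 2 women in the control group for every woman in the experimental group", and a final total of 72, "of which 24 will be from the experimental group and 48 the control". It mentions no allowance for clustering.

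Data analysis states: "In the case of the qualitative data, the Chi-square test will be used", with Fisher's exact test as the fallback and Student's t-test for means. Binary logistic regression for perineal trauma is to be adjusted for predictors that are not listed. District, centre, trainer and class are not named in that section, and no stratified or cluster-adjusted method is planned.

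**The concern.** Without randomisation, the two arms can differ in district mix by chance, by preference or through the supply of places. Trainer supply is itself uneven between the districts. Episiotomy depends partly on local obstetric practice. If practice differs between the two districts, an unadjusted test credits that difference to Pilates or hides a real effect behind it.

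A separate matter is independence. Women taught by the same trainer may have outcomes more alike than women taught by different trainers. The listed between-group tests take every woman as independent, so their 5% error rate and 95% intervals would not hold exactly.

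**Working it through.** **1. The planned sample size contains no design effect.** Inputs from Sample size: "considering 49% avoiding episiotomy in the control group in comparison with 98% in the experimental group", "for a confidence level of 95% and a power of 80"% (two-sided assumed), ratio 2:1. The pooled proportion is (0.98 + 2 × 0.49)/3 = 0.653.

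- Uncorrected n in the Pilates arm = [1.96 × √(1.5 × 0.653 × 0.347) + 0.842 × √(0.98 × 0.02 + 0.49 × 0.51/2)]² / 0.49² = 8.9, or 9 per arm and 27 in total.
- With the continuity correction, n = (8.9/4) × [1 + √(1 + 6/(2 × 8.9 × 0.49))]² = 11.8, so 12 + 24 = 36.

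This matches the stated minimum of 36 exactly, with independent women.

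**2. District mix, assuming no Pilates effect.** The documents give neither district rates nor the district split of the arms, so all inputs here are assumptions. Equal numbers per trainer would put 16 of 24 Pilates women (two thirds) in Huelva. The spurious difference is (Pilates share in Huelva − control share in Huelva) × district gap. The table shows Pilates minus control in the percentage avoiding episiotomy, with district rates placed around 49%. The direction (Huelva higher) is arbitrary.

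| Controls in Huelva | 10-point gap (54% / 44%) | 20-point gap (59% / 39%) |
|---|---|---|
| none | +6.7 points (OR 1.31) | +13.3 (OR 1.72) |
| one third | +3.3 (OR 1.14) | +6.7 (OR 1.31) |
| one half | +1.7 (OR 1.07) | +3.3 (OR 1.14) |
| two thirds | 0 | 0 |
| all | −3.3 (OR 0.87) | −6.7 (OR 0.76) |

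For example, one third and 20 points: 2/3 × 59 + 1/3 × 39 = 52.3%, against 1/3 × 59 + 2/3 × 39 = 45.7%. The bias is zero when the mix is equal and changes sign with it.

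**3. Clustering by trainer.** 24 women / 3 trainers = 8 on average. Controls have no trainer, so only the Pilates arm is clustered. The ICC is not given; 0.01 to 0.10 is assumed. The design effect is DE = 1 + 7 × ICC. The ratio of the correct to the naive standard error under the null is √[(DE/24 + 1/48)/(1/24 + 1/48)], and the true error is 2[1 − Φ(1.96/ratio)].

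| ICC | DE | SE ratio | True error, formula | Same, simulated | Simulated, centre effects only |
|---|---|---|---|---|---|
| 0.01 | 1.07 | 1.02 | 5.5% | 6.1% | 5.4% |
| 0.05 | 1.35 | 1.11 | 7.8% | 8.4% | 4.9% |
| 0.10 | 1.70 | 1.21 | 10.6% | 11.5% | 4.4% |

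The simulations are beta-binomial with a 49% rate and 200,000 runs; at ICC 0 the test rejects in 5.5%. The last column assumes six centres, each with 4 Pilates and 8 control women who share only a centre effect. There the naive test rejects less often as the ICC rises.

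**4. Power.** 36 × 1.70 = 61.2, or 62 women, still below 72. With 24 + 48 women and the stated rates, power stays above 99% over this ICC range.

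**The case against.** Several stronger readings are tempting, and the documents do not support them.

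- A reader might infer that Pilates is given in group classes. The text gives the number and length of sessions only, and Table 1 is not shown. Shared trainers are enough to make clustering possible, but not to establish it.
- A reader might infer that the intervals are certainly too narrow. That needs a positive trainer or class ICC, which the documents do not give. If centres hold both arms and only centre effects exist, the intervals may instead be slightly too wide.
- A reader might apply clusters of 8 to both arms, giving 2[1 − Φ(1.96/√1.70)] = 13.3% at an ICC of 0.10. Controls have no trainers, so that cluster size has no basis for them.
- A reader might take the Introduction's remark that "there is a disparity between the public and private systems" as evidence that Huelva and Seville differ. It compares types of provider, not these districts.
- A reader might say that the plan leaves district out altogether. The logistic covariates are unnamed, so district may be among them. What can be said is that it is not prespecified and that the chi-square, Fisher and t-tests do not use it.

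The plan also does something to limit variation in delivery: it restricts sites to centres with midwife-led classes and uses trainers of equivalent training. The largest objection is one of scale. If the true difference is near 49 points, neither district mix nor clustering of the size shown would change the conclusion. That stands, and it is why this is an improvement to make and not a fatal flaw. It gives no protection if the effect is modest, or for tears, for which no effect size is planned.

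**Conclusion.** The point holds in conditional form. The listed between-group tests are unadjusted and district is not prespecified anywhere in the analysis, in a non-randomised study where nothing equalises the district mix. Confounding by district is therefore possible, in either direction. It amounts to about 3 to 7 points if two thirds of Pilates women and one third of controls are in Huelva and the districts differ by 10 to 20 points. The trainer effect is less certain: an error of about 5.5% to 10.6% for a nominal 5% test, resting on an assumed ICC of 0.01 to 0.10, 8 women per trainer and unclustered controls. No consequence for the sample size follows, because 72 covers the inflation considered. The case for change rests on a known, easily recorded variable and a better method at little cost.

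**What to change.** In Data analysis:

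- Make the between-group comparison of episiotomy and perineal tear a district-stratified Mantel-Haenszel test, or its exact version if cells are sparse. Tear grade is ordinal, so state whether the ordinal extension or a prespecified binary cut is used.
- Name district as a fixed factor in the logistic model.
- Tabulate arm by district, centre and trainer, and record trainer for each Pilates woman.
- State as a limitation that three trainers cannot support a reliable cluster model. A cluster-robust sensitivity analysis is optional and would be only approximate.

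Where feasible, aim for the same 1:2 Pilates-to-control ratio in each district. This is a change to recruitment and not only to wording, so it should be a target and not a condition.

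The statistical cost is about one degree of freedom and slightly wider intervals. Strata may also be empty: at the planned 98%, only 24 × 0.02 = 0.48 episiotomies are expected in the Pilates group, so a stratified odds ratio may not be estimable. The plan should say what is reported in that case. These choices should be fixed before outcome data are seen, since adding district afterwards would look data-driven.

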#### Experimental group

The experimental group will receive two one-hour Pilates sessions per week over a period of 4 weeks (Table 1). In addition, the participants will receive their usual antenatal classes at their respective health centres in accordance with the Comprehensive Healthcare Programme for Pregnancy, Childbirth, and Postpartum (CHPPCP) from the Andalusian Regional Government (Aceituno et al. 2014).

#### Control group

The control group will receive solely the antenatal classes at their corresponding centres as programmed (Table 2).

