#### **Data Collection**

##### Outcomes

The dependent variables will be age (years), blood pressure (mmHg), weight (kg), BMI (kg/m^2), starting level of physical activity, and tobacco use. These variables will be all measured by experienced personnel at the start of the experimental phase, at two weeks, and again at four weeks after the treatment for both groups had been completed.

Variable relating to childbirth will be measured between the eighth and tenth day after birth by telephone interview and review of hospital medical history. The number of weeks of pregnancy at birth will be measured on a discrete

quantitative scale. Labour onset (spontaneous, stimulated, induced), type of delivery (spontaneous, assisted delivery with forceps, Thierry's spatulas or vacuum extraction, caesarean section), the use of intrapartum pharmacological analgesia (none, epidural anaesthesia, sedatives, nitrous oxide), type of episiotomy (not required, median, lateral, medio-lateral) will be measured by nominal scales, while the degree of perineal tear will be evaluated on an ordinal scale (no injury, degree I: injury to perineal skin; degree II: injury to perineal skin and muscle; degree III: injury to perineal skin, muscle and anal sphincter; degree IV: injury to perineal skin, muscle, sphincter and anorectal mucosa). Weight (kg) and height (cm) will be recorded during the routine antenatal appointments at the health centres using stadiometers with weight scale function. The level of physical activity will be measured using the International Physical Activity Questionnaires (IPAQ) (Craig et al. 2003).

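### Groups formed by invitation, with no record of Pilates or perineal massage outside the study, so unequal use or dilution would go unseen

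*Combined protocol and SAP*

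**What the plan says.** **Exposure.** The Control group section says "The control group will receive solely the antenatal classes at their corresponding centres as programmed". This describes what the study supplies. No section limits or checks what women in either group do elsewhere.

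**Group formation.** Participants describes a convenience sample. Interventions says women attending antenatal classes are invited into one group or the other. No random allocation, and no other allocation rule, is given.

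**Eligibility.** The only criterion in Participants that touches exercise is "there not being any contraindications for physical exercise". The exclusions cover missed appointments, language, caesarean birth and refusal.

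**Variables.** The nearest item in Outcomes is general activity: "The level of physical activity will be measured using the International Physical Activity Questionnaires (IPAQ"). The other items are age, blood pressure, weight, BMI, tobacco use and the childbirth variables.

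**Background.** The Background section opens one paragraph with "Given the marked increase in practising Pilates during pregnancy". The Introduction lists perineal massage from week 34 among effective preventive measures, "which has been found to diminish the number of episiotomies in primiparae".

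**Analysis.** Data analysis plans adjusted logistic models for perineal trauma but does not name the covariates.

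**The concern.** In a non-randomised comparison, the groups are balanced only by luck or by adjustment, and adjustment needs recorded data. Here two exposures that the plan itself treats as relevant to the perineum are not recorded. Two separate mechanisms follow.

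- **Confounding.** Women who already practise Pilates, or who do perineal massage, may be more willing to join the Pilates group. Their results would then be credited to the four-week programme. The bias could also run the other way: experienced women may have little left to gain, or massage may be more common among controls.
- **Dilution.** Controls who attend Pilates elsewhere narrow the contrast between the groups.

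The planned models cannot correct for something never asked, and a reader of the results could not tell whether either mechanism had operated.

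**Working it through.** **Step 1. Is either exposure restricted or recorded?**

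| Exposure | Participants | Outcomes | Data analysis |
|---|---|---|---|
| Pilates before or during the study, outside it | no criterion | not listed; IPAQ level only | covariates not named |
| Perineal massage | no criterion | not listed | covariates not named |

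An overall activity level does not identify Pilates and carries no information on massage.

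**Step 2. Reproduce the planned sample size.** Inputs from Sample size: "considering 49% avoiding episiotomy in the control group in comparison with 98% in the experimental group"; "a ratio of 2 women in the control group for every woman in the experimental group"; 95% confidence; 80% power. Sidedness is not stated; two-sided is assumed. With p1 = 0.98, p2 = 0.49, k = 2, d = 0.49:

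- Pooled rate = (0.98 + 2 × 0.49)/3 = 0.6533.
- n = [1.96 × √(1.5 × 0.6533 × 0.3467) + 0.842 × √(0.98 × 0.02 + 0.49 × 0.51/2)]² / 0.49² ≈ 8.9.
- With continuity correction: n' = (n/4) × [1 + √(1 + 2(k+1)/(n·k·d))]² ≈ 11.8, rounded up to 12.
- Total = 12 + 24 = 36, which matches the plan.

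**Step 3. Dilution (illustration).** Let c be the share of controls doing outside Pilates. The documents give no value, so c is assumed. Assume also that each such woman has the full 98% rate. Control rate = 0.49 + 0.49c; difference = 0.49(1 − c).

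| c (assumed) | Control rate | Difference (points) | N for 80% power | Fisher power, 12 + 24 | Fisher power, 24 + 48 |
|---|---|---|---|---|---|
| 0% | 49.0% | 49.0 | 36 | 92% | >99% |
| 10% | 53.9% | 44.1 | 42 | 85% | >99% |
| 20% | 58.8% | 39.2 | 51 | 74% | 99% |
| 30% | 63.7% | 34.3 | 60 | 59% | 97% |
| 40% | 68.6% | 29.4 | 75 | 41% | 92% |
| 50% | 73.5% | 24.5 | 93 | 23% | 81% |

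The N column uses the corrected formula of Step 2. The last column means all 72 women are analysed. The minimum of 36 falls below 80% by c = 20%.

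**Step 4. Confounding (illustration).** Suppose the programme has no effect of its own, and shares fE of the Pilates group and fC of controls were already trained and have the 98% rate. The false difference is 0.49 × (fE − fC).

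| fE, fC (assumed) | Rates | False difference (points) | Significant by Fisher at 24 + 48 |
|---|---|---|---|
| 20%, 0% | 58.8% v 49.0% | 9.8 | 10% |
| 30%, 10% | 63.7% v 53.9% | 9.8 | 11% |
| 50%, 10% | 73.5% v 53.9% | 19.6 | 34% |
| 50%, 0% | 73.5% v 49.0% | 24.5 | 50% |

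Equal shares give no bias in this model; imbalance is what matters. No similar sum can be done for massage, because the documents give no size for its effect.

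**The case against.** The strongest reply has four parts.

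- **Exercise is partly measured.** IPAQ is collected in both groups from baseline and adjusted models are planned. This is true, but it does not identify Pilates or massage.
- **The size rests on assumptions.** The shares are invented, the 98% rate for every outside practitioner is extreme, and if the 49% is a usual-care rate it already contains some background Pilates, so Step 3 would count that twice. This stands. The tables show how the bias behaves and are not estimates.
- **Power is hardly affected.** This stands for 72 women analysed. It does not stand if losses bring the number near 36.
- **Massage is not the intervention.** This stands. A control woman who does massage is rightly counted as not having had Pilates. Massage is a co-intervention open to both groups and biases the result only if its use differs. Tables 1 and 2 are not in the supplied text, so whether the classes teach it cannot be checked; class content would in any case not show individual use.

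A reader might also infer that pelvic-floor exercise is credited with the same benefit as massage. The Introduction ties only massage to episiotomy; it credits pelvic-floor exercise with less discomfort and less urinary incontinence. Nor do the documents say that every centre supplies women to both groups.

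**Conclusion.** The point holds as a gap in measurement: a plausible confounder and a plausible source of dilution are left uncollected in a comparison formed by invitation. The documents show an open risk, not that it occurred. Its size is unknown, since a marked increase in Pilates is asserted without a prevalence. Under the assumptions above, dilution costs 4.9 points per 10% of controls and leaves 97% power at c = 30% with 72 women. A false difference of about 10 to 25 points needs a 20- to 50-point imbalance in prior practice. Bias and interpretation are therefore the main issue.

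A reader might go further and infer that neither a null nor a positive result could be attributed to the programme. The documents do not support laying that on this gap: the limit on attribution comes mainly from the absence of randomisation, and would remain after the fix. A reader might also infer that women already doing Pilates must be excluded. That does not follow either. Comparison with usual care, background activity included, is a legitimate question, and recording the exposure meets the concern.

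The change is worth making because it is cheap and these histories are hard to recover reliably later.

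**What to change.** **Data Collection.** Ask both groups the same short questions on prior and current Pilates (or similar pelvic-floor training) and on perineal massage. Ask at baseline and repeat at the planned follow-up measurements, before birth where possible. Repetition matters because the plan dates massage from week 34, so a baseline answer may precede it. Leaving the questions to the interview on days 8 to 10 would let knowledge of the perineal outcome colour recall. Outcomes and Data analysis give different follow-up weeks; settle these so the contacts before birth are clear.

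**Data analysis.** Name baseline Pilates practice as a covariate in the logistic model for perineal trauma. Keep every woman in the group she entered. Report concurrent outside Pilates and massage by group. Add a sensitivity analysis that adjusts for massage in both groups. Do not remove exposed controls only: that selects on behaviour after entry in one group and can itself favour Pilates. Massage belongs in the sensitivity analysis because use after entry may be influenced by group.

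**Cost.** A few questions at existing contacts, and one or two more terms in a small model. On the planning rates about 48 × 0.51 + 24 × 0.02 ≈ 25 women would have an episiotomy, so the other covariates should be few and named in advance. No new eligibility criterion is needed.
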